#### 5.1 Registration with the University of Minnesota Clinical Trials Office

Any patient who is consented is to be registered in OnCore by the site Study Coordinator or designee.

If a patient is consented but is not enrolled in the study treatment (i.e. is found to be ineligible based on pre-transplant inclusion/exclusion criteria), the patient's record is updated in OnCore as a screen failure and reason for exclusion recorded.

Additional information is found in the study's Procedures Manual for Participating Sites.

In addition, participating institutions are responsible for fulfilling any local study registration requirements.

#### 5.2 Patient Enrollment to Study Treatment in OnCore

To be eligible for study treatment, the patient must sign the treatment consent and meet each inclusion criteria and none of the exclusion criteria on the eligibility checklist based on an eligibility assessment documented in the patient's medical record.

After transplant, the study doctor will need to assess the patient to determine if the criteria in Section 4.3 is met and continuing on the study is in the best interest of the patient based on their current medical situation.

The patient is assigned to the currently enrolling treatment plan after the transplant and confirmation of continuing eligibility.

#### 5.3 Patients Who Do Not Begin Study Treatment

If a patient is enrolled in the study (i.e. assigned a sequence number) and is later found unable to begin FT596, the patient will be removed from study and treated at the physician's discretion. The study staff will update OnCore of the patient's non-treatment status (off study) with the reason for removal from study prior to starting study treatment clearly indicated. The patient will be replaced to complete enrollment. Any data and research samples collected up to this point will be retained as detailed in the written consent document.

If a patient receives FT596, they are considered on treatment and most continue follow-up per Section 8.

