#### 6.6 Duration of Treatment

Treatment consists of a single dose of rituximab or an FDA approved biosimilar followed 2-3 days later by FT596 at the patient's assigned dose/schedule. If a patient cannot receive FT596 by 7 days after rituximab due to unresolved infusion related toxicity (refer to Section 6.1), FT596 is not given.

All patients receiving at least one dose of FT596 will be followed per Section 8.1.

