### 10 Adverse Event Monitoring, Documentation, and Reporting

For the purposes of the study the FT596 in combination with rituximab (Rituxan and FDA approved biosimilars) is considered the investigational product.

For the reminder of the section rituximab is a blanket term for Rituxan and any FDA approved biosimilars.

Toxicity and adverse events will be classified and graded according to NCI's Common Terminology Criteria for Adverse Events V 5.0 (CTCAE) and reported on the schedule below. A copy of the CTCAE can be downloaded from the CTEP home page. (https://ctep.cancer.gov/protocoldevelopment/electronic\_applications/docs/CTCAE\_v 5\_Quick\_Reference\_5x7.pdf) An exception to the use of CTCAE will be for the assessment of cytokine release syndrome (CRS). Individual adverse events which are associated with CRS will be graded per CTCAE; however the ultimate assessment will be made using a revised grading system for CRS as presented by Lee et al (Lee 2019).

ASTCT Cytokine Release Syndrome Consensus Grading System a								
CRS Parameter	Grade 1	Grade 2	Grade 3	Grade 4				
Fever b	Temperature ≥38°C	Temperature ≥38°C	Temperature ≥38°C	Temperature ≥38°C				
With either:								
Hypotension	None	Not requiring vasopressors	Requiring vasopressors with/with-out vasopressin	Requiring multiple vasopressors (excluding vasopressin)				
And/or c	•		•	· · · · ·				
HypoxiaNoneRequiring low-flow nasal cannula d or blow-byRequiring high-flow nasal cannula, facemask, non-rebreather mask, or venturi maskRequiring positive pressure (e.g., CPAP, BiPAP, intubation and mechanical venturi mask								

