#### **10.2 AE Documentation Requirements**

Adverse event collection for the purposes of this study will focus on events felt to be related to FT596 and rituximab or events that cannot be attributed to other causes (i.e. transplant-related, co-morbidities).

Monitoring for adverse events will begin with the first dose of rituximab through the End of Treatment visit after FT596.

Adverse event documentation for the purposes of this study will focus on

- expected toxicities felt to be related to rituximab
- expected toxicities felt to be related to the FT596
- unexpected adverse events that cannot be attributed to the transplant procedure or other causes (i.e. underlying disease, co-morbidities)

For the purposes of this study, adverse event documentation requirements in OnCore will be based on grade, expectedness and relationship to the investigational product (FT596 and rituximab):

	Grade 1	Grade 2		Gr	ade 3	Grade 4 and 5
	Expected or Unexpected	Expected	Unexpected	Expected	Unexpected	Expected or Unexpected
Unrelated Unlikely	Not required	Required	Required	Required	Required	Required
Possible Probable Definite	Not required	Required	Required	Required	Required	Required

After the End of Treatment visit, monitoring for adverse events will become less frequent based on the schedule in Section 8.1 and only events that are unexpected and at least possibly related to FT596 will be documented upon knowledge.

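### Patients given study rituximab but no FT596 leave the study with no defined adverse-event follow-up and no assured place in the safety tables

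*Combined protocol and SAP*

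**What the plan says.** Section 5.3 covers an enrolled patient who is "later found unable to begin FT596, the patient will be removed from study and treated at the physician's discretion". Study staff mark the patient in the database as untreated and off study, "with the reason for removal from study prior to starting study treatment clearly indicated". It then adds: "The patient will be replaced to complete enrollment". It also says: "Any data and research samples collected up to this point will be retained as detailed in the written consent document". The counterpart rule is: "If a patient receives FT596, they are considered on treatment". None of this distinguishes a patient who has had no study drug from one who has already had study rituximab.

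Section 6.6 defines treatment as one rituximab dose followed by FT596, and says that FT596 is not given if rituximab infusion toxicity still prevents it 7 days after rituximab. It closes: "All patients receiving at least one dose of FT596 will be followed per Section 8.1".

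Section 10 says: "For the purposes of the study the FT596 in combination with rituximab (Rituxan and FDA approved biosimilars) is considered the investigational product". Section 10.2 says: "Monitoring for adverse events will begin with the first dose of rituximab through the End of Treatment visit after FT596". It lists toxicities attributed to rituximab among the events to document. The calendar in Section 8.1 puts the End of Treatment visit at day 28, counted from the FT596 infusion.

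Section 10.3 requires every serious AE (SAE) to be documented, whichever study drug was received. Section 10.4 counts only events after FT596 towards dose-limiting toxicity (DLT) and the stopping rules. Section 12.3 says that safety will be estimated descriptively and names no analysis set.

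**The concern.** The protocol requires the rituximab dose, counts it as investigational product and monitors for its toxicity. It also foresees that this toxicity can prevent FT596. The patients who take that path are the ones whose planned observation ends, and it ends because the toxicity has not resolved. The loss of follow-up is therefore informative.

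The eventual outcome, duration and peak grade of the event, and anything that develops later, fall outside defined collection. The first secondary objective describes AEs of FT596 given in combination with rituximab. In a descriptive summary of 12 to 18 patients per component, one patient who could not complete the regimen because of rituximab toxicity is worth reporting in full. The database label of untreated makes it easy to leave that patient out of a table of treated patients.

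**Working it through.** No sample size, power or error rate lies behind this point, so there is no plan figure to reproduce. The check sets the sections side by side and then gauges the scale.

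**1. Is a rituximab-only patient treated?** Under Sections 6.6 and 10, treatment and the investigational product include rituximab. Under Section 5.3, a patient is on treatment once FT596 is given, and removal before that is recorded as preceding study treatment. Both cannot hold for a patient who has had rituximab.

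**2. Can it happen?** Yes. Sections 6.1.2 and 6.6 allow FT596 to be delayed up to 7 days for rituximab infusion toxicity to settle, and otherwise FT596 is not given. Failing a Section 4.3 criterion after rituximab could lead to the same place for other reasons.

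**3. What is captured before removal?** AE monitoring has begun, data are retained, the reason for removal is recorded and SAEs are documented. The blocking reaction should be on file.

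**4. What is captured afterwards?** Section 6.6 assigns the Section 8.1 follow-up to FT596 recipients. The Section 10.2 window closes at a visit that this patient never has. Section 10.3 gives no collection period for a patient who is off study. Section 10.5 covers deaths during treatment and follow-up, and neither period is defined for this patient. Section 3 heads its one-year follow-up as applying to all patients, which adds to the ambiguity.

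**5. Length of observation.** An FT596 recipient on schedule is monitored for 2 + 28 = 30 to 3 + 28 = 31 days after rituximab. A patient removed at the 7-day limit (assumed removal day) has 7 days. The shortfall is 30 − 7 = 23 to 31 − 7 = 24 days.

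**6. Component 2 timing.** For FT596 on Day 7, rituximab falls on Day 7 − 3 = Day 4 to Day 7 − 2 = Day 5. With the +3 day window, the latest is Day 10 − 2 = Day 8. Removal 7 days later is then Day 11 to Day 15 post-transplant. Section 2.5 cites median neutrophil recovery at Day 10 and platelet recovery at Day 19. Removal therefore comes before the Day 28 engraftment check and before median platelet recovery.

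**7. Scale.** Let q be the probability that a patient given rituximab does not receive FT596. The documents give no value, so 1% to 10% is an assumption for illustration. With n patients treated with FT596 in a component (12 most likely, 18 maximum, Section 12.2):

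- expected number removed = n × q / (1 − q); for example 18 × 0.10 / 0.90 = 2.0
- chance of at least one = 1 − (1 − q)^n; for example 1 − 0.99^12 = 11.4%

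| n | q | Expected removed | Chance of at least one |
|---|---|---|---|
| 12 | 1% | 0.12 | 11.4% |
| 12 | 5% | 0.63 | 46.0% |
| 12 | 10% | 1.33 | 71.8% |
| 18 | 1% | 0.18 | 16.5% |
| 18 | 5% | 0.95 | 60.3% |
| 18 | 10% | 2.0 | 85.0% |

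**The case against.** A reader might infer that the worst rituximab toxicities drop out of the safety data, so that, say, 1 affected patient in 13 would be reported as 0 in 12. The documents do not support that. Section 5.3 retains the data and the reason for removal, and Section 10.3 captures any SAE. Section 12.3 does not exclude these patients; it is silent. The 1-in-13 example needs both an assumed rate and an assumed exclusion. Nor does the rule select the worst reactions: it turns on toxicity not having settled to Grade 1 or less within 7 days. A severe reaction that resolves quickly does not trigger it, and a persistent Grade 2 reaction does.

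Three further objections carry weight.

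- The number affected may be zero. Section 9.2 describes first-infusion reactions as commonly mild and serious ones as rare, and Section 4.2 excludes patients unable to receive rituximab. The low end of the assumed range is plausible.
- A patient without FT596 cannot contribute an FT596-related event, and counting only post-FT596 events for DLT and stopping is an explicit design choice. Both stand, and the point leaves them alone. Sections 10 and 10.2 nevertheless bring rituximab toxicity within the safety collection.
- Cytopenia or infection soon after conditioning would often be put down to the transplant, and is not itself the trigger in Section 6.6. This stands, and it limits how much the Component 2 timing adds.

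What the objections do not answer is the period after removal. Retention covers only what was collected up to that point, and no section states how long such a patient is observed or where the patient is reported.

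**Conclusion.** The point holds in a narrow form. Sections 5.3, 6.6, 10 and 10.2 disagree on whether a patient given study rituximab but no FT596 has been treated and is still monitored. If Section 5.3 is followed as written, planned follow-up ends while the toxicity that blocked FT596 is unresolved, about 23 to 24 days short of what an on-schedule FT596 recipient gets, taking removal at day 7. The AE window has no end point for this patient, and inclusion in the safety tables is possible but not assured.

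At assumed rates of 1% to 10%, about 0.1 to 2 patients per component are expected, and possibly none. The maximum tolerated dose, DLT evaluation and stopping rules are unaffected. This is an inexpensive improvement to make before reporting, not a threat to the primary objective.

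**What to change.** Reconcile Sections 5.3, 6.6 and 10.2 by splitting the rule.

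- A patient removed before any study drug goes off study, as now.
- A patient given study rituximab but no FT596 is still replaced for the continual reassessment method and still does not count for DLT or stopping rules. The patient stays under AE, SAE and death collection until 28 days after rituximab, or until the event resolves if that takes longer. The data are abstracted from standard-of-care visits, including Day 28 engraftment status in Component 2 where available. The database status distinguishes this patient from one who received nothing.

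In Section 12.3, define a safety set of all patients given any study rituximab or FT596, and list rituximab-only patients separately with the reason FT596 was not given.

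The cost is protocol wording and a little chart abstraction for few or no patients. No dose, treatment rule or dose-finding calculation changes.

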#### 6 Treatment Plan

Primary supportive care is to continue according to the primary transplant protocol. In order to provide optimal patient care and to account for individual medical conditions, investigator discretion may be used in the prescribing of all supportive care drug therapy (i.e. acetaminophen, diphenhydramine, antimicrobials, etc.).

Because they may inhibit NK cell function, systemic corticosteroids should be avoided during the treatment period (3 days before and through 14 days after FT596) unless absolutely required. Intravenous glucocorticoid as premedication for rituximab may be administered per the USPI or institutional guidelines. Methylprednisolone should be used as preferred glucocorticoid premedication given its shorter half-life.

Treatment may be given as an inpatient or an outpatient. There is no protocol driven requirement for hospitalization.

For scheduling purposes, the rituximab/FT596 "package" is administered with a +3 day window from the targeted FT596 administration day (Day 30 or Day 7). Rituximab or an FDA approved biosimilar is given 2-3 days (48 to 72 hours) prior to the planned FT596 infusion.

# 6.1 Rituximab or an FDA Approved Biosimilar and FT596 Administration General Guidelines

Rituximab or an FDA approved biosimilar and FT596 are administered in the same manner regardless of FT596 dose and the administration days. Refer to the following sections for detailed information including enrollment plan, definition of dose limiting toxicity and early study stopping events.

- Section 6.2 Component 1: Identify FT596 MTD when given on Day 30 only.
- Section 6.3 Component 2: Determine the MTD and safety of Day 7 FT596.

# 6.1.1 Rituximab or FDA Approved Biosimilar (2-3 days prior to each FT596 Administration)

Rituximab (Rituxan or an FDA approved biosimilar, e.g. Truxima and Ruxience) 375 mg/m^2 is administered as an IV infusion per institutional practice and the specific product's package insert on 2-3 days (48 to 72 hours) prior to the FT596. Pre-medications and supportive care per institutional standard of care guidelines.

#### 6.1.2 FT596 Administration

FT596 is given 2-3 days after rituximab; however, it may be delayed for up to 7 days until all rituximab infusion related toxicities resolve to ≤Grade 1.

**FT596 Thawing Overview:** FT596 is provided in one or more cryopreserved bags based on the patient's dose level. The correct number of bags are transferred to the site of infusion using a validated cooler. Thawing occurs on the unit just prior to administration. When dose level requires multiple bags, bags are thawed sequentially. FT596 is stable for up to 60 minutes post-thaw. Administration of the cell product must begin within 60 minutes of thawing.

**FT596 Infusion guidelines:** FT596 must be administered via gravity using a Fate approved IV administration set with an in-line filter. Total infusion time per bag is less than 10 minutes. If multiple bags are used, a short delay between infusions occur to allow for product thawing. To infusion 3 bags of cells (the maximum required for the dose levels in this study), total infusion time from the start of the 1st bag to the end of the last bag would be 30-40 minutes.

Complete information is provided in the FT596 Storage, Handling, and Administration Guidance

The end of administration time should be recorded after the rinse step has been completed. When the study drug administration has been completed, discard the empty study drug bag/tubing in accordance with local site policy.

**Pre-Medications**: Prior to administration of FT596 and 4-6 hours later, patients should be pre-medicated with acetaminophen 650 mg orally (PO) and diphenhydramine 25 PO. Corticosteroids should not be used as pre-medication for FT596.

**Vital Signs:** Vital signs (temperature, systolic and diastolic blood pressure, heart rate, and respiration rate) are performed in association with the FT596 infusion at the following time points: within 15 minutes of the infusion start, at 10 ( $\pm$ 5) minutes during infusion, and every 15 ( $\pm$ 5) minutes for 1 hour after the end of the last administered bag of FT596.

**Collection of research sample 30 (±5) minutes after the last bag of FT596** is infused per Section 8.2. One or more bags are given depending on the dose level.

**Monitoring for Infusion Related Reactions:** All patients are monitored for signs of an infusion related reaction. The highest grade infusion reaction for the FT596 infusion must be documented (and if applicable reported as a dose limiting toxicity and/or an SAE).

Refer to Section 7.1 for the management of any grade of an infusion related reaction.

If a Grade 3 or 4 infusion related reaction occurs (defined as CTCAE v 5.0 – prolonged or life-threatening consequences), the infusion is stopped if possible (i.e. no additional bags of cells are given) and the patient receive supportive care per Section 7.1 guidelines. The patient will receive no further FT596. All patients are monitored for adverse events, dose limiting toxicity and death per Section 10.Refer to Section 7 for management of FT596 related toxicity.

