# If Grade 4 Infusion-Related Reaction (Life-threatening consequences; urgent intervention indicated):

Stop FT596 administration. Do not restart.

The volume of FT596 administered prior to the infusion-related reaction must be documented; retain any remaining product and contact [name] or designee for further instructions.

If Grade ≤3 Infusion-Related Reaction (e.g., not rapidly responsive to symptomatic medication and/or brief interruption of infusion); recurrence of symptoms following initial improvement; hospitalization indicated for clinical sequelae):

- Interrupt FT596 administration.
- Manage symptoms, e.g., with antihistamines, antipyretics and analgesics, according to standard institutional practice standards.
- Resume FT596 administration only upon complete resolution of the infusionrelated reaction and at the discretion of the Investigator. Given that FT596 administration may involve single or multiple bags depending on the total planned dose and accounting for the stability of FT596 post-thaw, FT596 administration may continue following resolution to a Grade 1 infusion-related reactions as follows:

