#### If single-bag FT596 dosing:

- No additional FT596 may be administered.
- The volume of FT596 administered prior to the infusion-related reaction must be documented; retain any remaining product and contact the Study PI (or designee) for further instruction.
- Additional bags may not be administered to make up for FT596 that was not administered from the bag during which the infusion-related reaction occurred.

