#### If multiple-bag FT596 dosing:

- The volume of FT596 administered from the bag during which the infusionrelated reaction occurred must be documented; retain any remaining product from the bag and contact the Sponsor for further instruction.
- If dosing with additional FT596 bags was planned, they may be thawed and administered.
- Additional bags beyond what was originally planned may not be administered to make up for FT596 that was not administered from the bag during which the infusion-related reaction occurred.

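### After a Grade 3 FT596 infusion reaction in multiple-bag dosing, Section 6.1.2 forbids further cells while Section 7.1 allows the remaining bags

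*Combined protocol and SAP*

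**What the plan says.** Section 6.1.2 (FT596 Administration) sends the reader to Section 7.1 for managing infusion reactions of any grade. It then gives its own rule for Grade 3 or 4: "the infusion is stopped if possible (i.e. no additional bags of cells are given", followed by "The patient will receive no further FT596". For those grades it refers to Section 7.1 for supportive care.

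Section 7.1 divides the grades differently. Stopping without restart applies to Grade 4. The other branch opens "If Grade ≤3 Infusion-Related Reaction (e.g., not rapidly responsive to symptomatic medication and/or brief interruption of infusion", and its description goes on to recurring symptoms and a need for hospitalization. In that branch the infusion is interrupted and symptoms are treated. Two conditions for continuing then appear in the same bullet: "Resume FT596 administration only upon complete resolution of the infusionrelated reaction and at the discretion of the Investigator" and "administration may continue following resolution to a Grade 1 infusion-related reactions".

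What may follow depends on the number of bags. For a single bag: "No additional FT596 may be administered". For several bags: "If dosing with additional FT596 bags was planned, they may be thawed and administered".

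Sections 6.2 and 6.3 list an infusion reaction of Grade 3 or higher as a DLT in both components. Section 7 states that there are no clinical data on FT596.

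**The concern.** The same bedside event receives opposite instructions. A site that reads Section 7.1 could give more cells to a patient who has just had a DLT, which Section 6.1.2 forbids. A site that stops complies with both sections; a site that resumes complies with one and breaches the other.

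The study is multi-center and dosing may be outpatient, so sites could handle the same reaction differently. Resumption is also practicable: "When dose level requires multiple bags, bags are thawed sequentially", so later bags may still be frozen when the reaction occurs. If the further bags turned a Grade 3 reaction into a Grade 4 one, Section 12.4.3 would also halt enrollment.

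**Working it through.** The plan gives no figure on this point, so the check compares the two sections case by case.

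**Where the sections agree and where they do not**

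| Reaction | Section 6.1.2 | Section 7.1 | Agree? |
|---|---|---|---|
| Grade 4 | Stop, no further FT596 | Stop, no restart | Yes |
| Grade 3, single bag | Stop, no further FT596 | Nothing more from that bag, no replacement | Yes |
| Grade 3, several bags, reaction in the last | Stop, no further FT596 | Rest of that bag retained, none left to give | Yes |
| Grade 3, several bags, bags remaining | Stop, no further FT596 | Remaining planned bags may be given after resolution | **No** |

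The conflict needs three things together: exactly Grade 3, a multiple-bag dose, and bags still to be given.

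**How much product is in dispute**

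Inputs: Section 6.1.2 gives three bags as the most any dose level needs. Section 7.1 has the site retain what is left of the bag in use at the reaction. For a reaction in bag k of n, the further bags allowed are 0 under Section 6.1.2 and n − k under Section 7.1. If bags are equal, the disputed share of the dose is (n − k)/n.

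| n | k | Section 6.1.2 | Section 7.1 | Disputed share, equal bags |
|---|---|---|---|---|
| 1 | 1 | 0 | 0 | 0% |
| 2 | 1 | 0 | 1 | 1/2 = 50% |
| 2 | 2 | 0 | 0 | 0% |
| 3 | 1 | 0 | 2 | 2/3 = 67% |
| 3 | 2 | 0 | 1 | 1/3 = 33% |
| 3 | 3 | 0 | 0 | 0% |

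The sections conflict in 3 of the 6 positions. This counts cases and is not a probability. The documents do not say that any dose uses two bags; without those rows the count is 2 of 4.

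Cells per bag, and which dose levels need more than one bag, are not stated. If the 9×10^8 level uses three equal bags, the largest disputed amount is 2/3 × 9×10^8 = 6×10^8 cells. With unequal bags the share could be anything from just above 0% to just under 100%.

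**Effect on dose finding**

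The reaction is a DLT before the two sections diverge. The patient enters the continual reassessment method as a DLT at the assigned level whether or not more bags follow. The updated toxicity estimates and the MTD recommendation are therefore the same either way.

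**The case against.** The strongest reply is that the sections can be reconciled. Section 6.1.2 states a specific, mandatory prohibition for Grade 3 or 4, while Section 7.1 only permits. On ordinary reading the specific prohibition controls, and no site faces two mandatory orders that cannot both be obeyed. That reading is sensible, but the documents do not state it, and Section 6.1.2 itself directs staff to Section 7.1 for every grade. Nor do the words in Section 6.1.2 about stopping where possible soften the rule: the sentence barring further FT596 is unconditional and, in a single-dose study, can only mean the rest of that dose.

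A second reply is that Section 7.1 meant Grade 2 or lower. This may be a slip, but the branch describes severe reactions: slow to respond, recurring, or needing hospitalization. Nothing elsewhere corrects it.

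Third, there are safeguards. Resumption requires resolution and investigator discretion, and Section 7.1 has the site contact the sponsor. The first two stand: re-exposure is permitted, not required, and comes only after recovery. The contact step attaches to product left in the partly used bag and is not a condition for hanging the next one.

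Fourth, the event should be uncommon. A three-bag infusion takes 30 to 40 minutes, and a prolonged reaction may not resolve soon enough for anyone to want to continue. This is fair, and the documents give no frequency. The separate handling guidance cited in Section 6.1.2 might also address bag contents or restarting; it was not available for this review.

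**Conclusion.** The concern holds. For a Grade 3 infusion reaction with bags remaining, the protocol both forbids and permits further FT596 and does not say which instruction prevails. The disputed product is up to two of three bags, or 33% to 67% of the assigned dose if bags are equal, an assumption the documents neither support nor exclude. Section 7.1 is also inconsistent within itself on how far the reaction must resolve.

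The trigger is narrow, and neither the DLT count nor the MTD is affected. The correction is still a must: the reaction is DLT-level, the protocol reports no clinical data on the product, and the wrong reading exposes a patient to more of it. The conclusion rests on the text alone and does not depend on the bag arithmetic.

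**What to change.** Amend Section 7.1 to match the rule in Section 6.1.2:

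- Limit the interrupt-and-resume branch to Grade 2 or lower, and rewrite its description so that prolonged, recurring or hospitalized reactions no longer sit there.
- Require a permanent stop for Grade 3 or higher, whatever the number of bags.
- Keep one criterion for resuming: either complete resolution or recovery to Grade 1.
- Report the volume delivered alongside the DLT data.

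This is a wording change to one section. It needs no new data, because Section 7.1 already requires the volume to be documented. The drawback is that some patients whose Grade 3 reaction resolves will not receive their full planned dose, as Section 6.1.2 already provides.
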